5.3 Birth Outcome Evaluations

For each subject, pertinent medical records were reviewed after delivery to determine maternity outcomes such as Expected Delivery Date and Birth weight. In addition, other delivery details such as delivery route, pregnancy complications, medications, etc. and neonate variables such as Apgar score, length, evidence of congenital anomalies, etc., were recorded as additional information.

5.4 Safety Measurements

Safety was assessed by the collection of volunteered adverse events experienced during the study period or observed by the examiner during the gingivitis exams.

The description of an AE included:

- Onset and resolve dates,
- Expectedness of the AE,
- Severity (Mild, Moderate, or Severe),
- Outcome (if known, whether or not AE was resolved or had a fatal outcome),
- Investigator's opinion as to the causality from the study medication (Doubtful, Possible, or Probable),
- Action taken regarding study medication,
- Indication of serious outcome (for each AE, the Investigator must determine if it is an SAE),
- Category of the AE (Non-Oral or Oral Category), and
- Whether the AE was reported by the subject or observed by the examiner.

5.5 Rules and Conventions for Analyses

All data will be checked for accuracy, completeness, and compliance with the study protocol prior to breaking the treatment blind. The statistical analyses are the responsibility of the Sponsor's Department of Global Statistics and Data Management Department. In addition, a statistical analysis plan will be completed by the Sponsor prior to breaking the treatment blind. All statistical analyses will be performed using SAS®.

There are 2 evaluable populations, one for Birth outcomes and one for Gingivitis outcomes, since the evaluability criteria are different for the two sets of variables. A subject can be non-evaluable for partial data (e.g., birth outcomes only, all monthly gingivitis outcomes, or only specific monthly gingivitis outcomes). The criteria for evaluability are outlined in Section 5.6. There will be one population for Intent-to-Treat, which is defined as those subjects who were randomized and received study product

5.6 Subject Evaluability Criteria for Randomized Subjects

5.6.1 Evaluability for Birth Outcomes

Subjects' birth outcome data (e.g. gestational age (GA), birth weight) will be assessed for evaluability based on the following criteria:

- 1) Drops: Declare as non-evaluable those subjects who were randomized and dropped from the study
- 2) Visit and Product Criterion
For purposes of evaluability, a *missed visit* occurred when an eligible subject (still pregnant) did not attend a visit.
 - a) Visit Criterion: Declare as non-evaluable those subjects who *missed 2 or 3* eligible post-baseline monthly visits.
 - b) Product Criterion (% of entire pregnancy with product): If the supply of products was less than 33.3% of the duration of the subject's entire pregnancy, then that subject will be non-evaluable.
- 3) Failed Entrance Criteria: Subjects who failed any entrance criteria at Baseline will be non-evaluable
 - Autoimmune disease
 - Type 2 Diabetes
 - > 24 weeks GA
 - < 30 bleeding sites
- 4) Failed Continuance Criteria: Subjects who had any of the following will be non-evaluable
 - Evidence/documentation of consistent non-compliance with assigned test product use (either from general comments or continuance criteria)
 - Elective termination of pregnancy
- 5) Pre-existing Condition: Subjects who had any of the following diseases/conditions or treatments that may impact GA will be non-evaluable
 - Uterine Abnormality (medically-significant)
 - Rh Incompatibility (untreated)
 - Previous Classical C-Section
 - Sickle Cell Disease
- 6) Adverse Event: Subject who had the following treatments that may impact GA will be non-evaluable

- Emergency C-Section with concomitant appendectomy due to stump appendicitis
- 7) Congenital Anomaly: Subjects who had the following medically significant congenital anomalies that may impact GA will be non-evaluable
- Trisomy 21
 - Fetal Hydrocephalus
 - Tetralogy of Fallot

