## 3. Overall Study Design and Plan

This is a multicenter randomized, controlled, single-blind, 2-treatment, parallel group clinical trial to assess gingivitis and maternity outcomes in pregnant women who undertake an advanced daily oral hygiene program. Up to 750 subjects will be enrolled to complete the study with a target population of approximately 600 evaluable subjects. Subjects will be adult female volunteers with moderate-to-severe gingivitis who are in the late first trimester or early-to-mid second trimester of pregnancy. Sufficient screening will be conducted to enroll approximately 300 subjects at each of two study centers. After informed consent and baseline measures are recorded, qualifying subjects will be randomly assigned in equal numbers to either 1) an advanced oral hygiene regimen consisting of marketed toothbrush. toothpaste, mouth rinse and floss plus oral hygiene education counseling, or 2) regular oral hygiene with an anticavity toothpaste, regular manual toothbrush and floss. Prenatal care will remain unchanged as part of study participation, following existing medical and institutional standards for treatment. Studyrelated evaluations will be scheduled, where possible, as part of routine prenatal visits, examinations will be conducted at Baseline before study product assignment, and monthly thereafter for 3 consecutive months of study product use. The primary outcome will be gingivitis and other clinical periodontal measures and samples will be collected. Adverse events will be collected from examination and interview. Oral hygiene and prenatal knowledge and practices will be assessed by survey at Baseline and Month 3. After Month 3, assigned oral hygiene products will be dispensed at prenatal visits or via home shipment through delivery. Maternity outcome data (gestational age) will be abstracted separately from medical records as a secondary variable, and other ancillary maternity data will be collected. An interim analysis of primary and secondary outcomes will be performed. The target population size and number of investigative sites may be adjusted as a result of the interim analysis. An independent Data Safety Monitoring Board will assess study design, conduct and outcomes at prescribed intervals using standard methods with respect to study integrity and continuance.

Table 1. Study Schedule by Procedure Type and Visit

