#### 9. Blinding, Labeling, and Shipping Plan

This is a single-blind study with limited access to the randomization code. Access to the treatment codes will be managed by the Sponsor's clinical supplies organization. The treatment each subject will receive will not be disclosed to the Principal Investigator, examiners, study center personnel, subjects, contracted monitors, contracted vendors, or the Sponsor, except for select site personnel responsible for usage instruction and supervised use, and the Data Safety Monitoring Board.

The identity of the toothpastes, mouth rinse and dental floss will be disguised. The identity of the powered toothbrush will not be disguised. All control kits will contain toothpaste, a manual toothbrush, dental floss and written instructions. Regimen kits will contain toothpaste, mouth rinse, a powered toothbrush, brush head, dental floss and written instructions. Additionally, supplemental kit boxes will be provided should additional kit boxes be needed to replace a kit box. Supplemental kit boxes may be dispensed only after consulting with the Sponsor for correct supplemental kit box assignment: the subject

identification number and original kit box number must be provided to the Sponsor and the Sponsor will provide the supplemental kit box number to be dispensed.

Kit boxes will be provided with a 1 month supply of study products to be dispensed at each of the first 3 study visits and a 16-week supply will be provided to be dispensed at the fourth study visit. The regimen and control kit boxes, including supplemental kit boxes, will be identically sized; the kit box labels will be identical except for a unique kit number used for assignment. Kit boxes will be packed in a randomized fashion based on a computer-generated randomization. An encrypted randomization file used by the B&A program links kit box number and treatment assignment.

All kit box labels will contain the study number, emergency phone number, distributor name/address, appropriate caution statements, content statement and other information as required by internal regulations and clinical SOPs. Kit box content statement will be worded to maintain the study blind. The shipping containers/pallets will be labeled with the clinical site address and a content statement listing the study number and kit box numbers contained within.

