2. STUDY OBJECTIVES AND DESIGN

This is a multicenter randomized, controlled, single-blind, 2-treatment, parallel group clinical trial to assess gingivitis and maternity outcomes in pregnant women who undertake an advanced daily oral hygiene program. Up to 750 subjects were to be enrolled to complete the study with a target population of approximately 600 evaluable subjects. Subjects were adult female volunteers with moderate-to-severe gingivitis who were in their late first trimester or early-to-mid second trimester of pregnancy (8-24 weeks of pregnancy).

Sufficient screening was conducted to enroll approximately 300 evaluable subjects at each of two study centers. After informed consent was obtained, the baseline measures were recorded and subjects were randomized to either: 1) an advanced oral hygiene regimen consisting of marketed rechargeable toothbrush, toothpaste, mouth rinse and floss plus oral hygiene education counseling (Regimen), or 2) regular oral hygiene with an anticavity toothpaste, regular manual toothbrush and floss (Control).

Separate randomizations were generated for each study site with approximately equal numbers of subjects randomized to both groups. Each randomization was balanced for history of pre-term birth, smoking status and number of bleeding sites.

Study-related evaluations were scheduled, where possible, as part of routine prenatal visits. Dental examinations were conducted at Baseline before study product assignment, and monthly thereafter for 3 consecutive months of study product use. Product distribution took place at the monthly visits or via shipment when the subjects were not present for the monthly evaluation. Adverse events were collected from examination and interview. Oral hygiene and prenatal knowledge and practices were assessed by survey at Baseline and Month 3 visit.

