The monthly gingivitis endpoints were the primary outcome measure, with the Month 3 evaluation being the primary time point of interest. Maternity outcome data (gestational age, birth weight, etc.) were abstracted separately from medical records as secondary variables with gestational age being of most importance. An interim analysis of the primary and secondary outcomes was performed by an independent statistician, and the target population size was adjusted. An independent Data and Safety Monitoring Board has assessed study design, conduct and outcomes at prescribed intervals with respect to study integrity, subjects' safety and evaluability.

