6.0. Statistical Methods and Determination of Sample Size

All statistical tests will be 2-sided tests except where noted; and any treatment difference p-values less than 0.05 will be cited as statistically significant. The analysis for the evaluable population will be considered as the primary population and the Intent-to-Treat (ITT) analyses will be considered secondary.

The primary test will be the treatment effect test for 3-month change from baseline for Löe-Silness. No adjustments for multiple testing will be employed.

All statistical tests will be carried out using SAS® version 9 (SAS Institute Inc., Cary, NC).

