6.4 Birth Outcome Endpoints

Null Hypothesis: There is no difference between treatment groups with respect to the mean birth outcome when an adjustment is made for baseline demographic variables (e.g. smoking, evidence of preterm birth, etc.)

Alternative Hypothesis: There is a difference between treatment groups with respect to the mean birth outcome when an adjustment is made for baseline demographic variables (e.g. smoking, evidence of preterm birth, etc.)

Statistical analyses to determine treatment differences for mean Gestational Age and mean Birth weight will be analyzed using an analysis of variance (ANOVA) model with demographic factors such as previous pre-term birth (< 37 weeks; Y/N), self-reported smoking during pregnancy (Y/N), mother's weight at delivery (in grams), Study site and treatment. Interactions of these demographic variables with treatment will also be investigated for inclusion into the model. If the interactions are not significant at the 10% level then they will be eliminated from the final model. 95% confidence intervals will also be generated on the treatment difference of the mean gestational age and mean birth weight.

If any of the data does not satisfy the normality criterion, then transformations will be considered to improve normality or analogous nonparametric methods will be employed.

In addition, gestational age will be categorized as preterm (gestational age < 37 weeks) or term (gestational age \geq 37 weeks) for subsequent analyses and tested for treatment differences using logistic regression with the same demographic factors as described above. Gestational age will also be analyzed for treatment differences as a time-to-event variable using the log-rank test (and Kaplan Meier curves) and Cox Regression (adjusting for demographics/covariates). Other categorizations may also be used to identify early preterm births: 20 to < 34 weeks (early preterm), 34 to <37 weeks (late preterm), \geq 37 weeks; or low birth weight (< 2500 grams).

The distribution of birth weight will also be generated within the following gestational age categories (< 34, 34 to <35, 35 to <36, 36 to <37, 37 to <38, 38 to <39, \geq 39 weeks) for each treatment group using box plots.

Additional subgroups may be defined for analyzing birth outcome data, such as the following:

- By Study Site
- By Race (Caucasian, Black, Other)
- By Gestational Age at enrollment (8 to \leq 12 weeks, >12 to \leq 16 weeks, >16 to \leq 20 weeks, >20 to \leq 24 weeks)

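### The product-supply rule for birth outcomes divides by the whole pregnancy, so late-enrolled women who were never without product leave the primary analysis set because they delivered early

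*SAP*

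**What the plan says.** SAP 5.6.1, criterion 2(b), sets the supply rule for the birth-outcome evaluable set: "If the supply of products was less than 33.3% of the duration of the subject's entire pregnancy, then that subject will be non-evaluable". Its label describes the quantity as the percentage of the entire pregnancy with product, but supply itself is not defined.

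SAP 6.0 gives this set its weight: "The analysis for the evaluable population will be considered as the primary population", with ITT secondary. SAP 2 describes the birth outcomes "as secondary variables with gestational age being of most importance". Under SAP 6.4, gestational age is analysed as a mean, as time to event, and as preterm versus term, the last "tested for treatment differences using logistic regression with the same demographic factors as described above". Births at 20 to <34 weeks may also form a category of their own.

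On supply, Protocol 4 admits women at 8 to 24 weeks, and the first products are given at Baseline. Protocol 9 provides a "1 month supply of study products to be dispensed at each of the first 3 study visits" and a 16-week supply at the fourth. Protocol 3 adds that after Month 3 "assigned oral hygiene products will be dispensed at prenatal visits or via home shipment through delivery". SAP 2 says product also went out "via shipment when the subjects were not present for the monthly evaluation".

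The interim analysis (SAP 3) used a different denominator: enough product for two thirds of study participation.

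**The concern.** The ratio depends on two things unrelated to whether a woman had her product: how far along she was at enrolment, and when she delivered. Weeks before enrolment count in the denominator but can never count as supplied. A short pregnancy leaves less time to make up for them. A late enrollee who always had product can therefore fail the rule solely because she delivered early.

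That makes membership of the primary birth-outcome set depend on gestational age at delivery. If the regimen changes the timing of birth, removal differs between arms and the comparison is no longer the randomised one. The women removed are concentrated among the earliest births, which are the events of most interest. Criterion 2(a) avoids this problem, because it counts a missed visit only while the woman is still pregnant. Criterion 2(b) has no such protection.

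**Working it through.** **1. The plan's own gestational-age figure.** Protocol 11 and SAP 6.8 give SD 4.1, a difference of 1.1 weeks, 90% power and two-sided 5%. Then n = 2 × (1.96 + 1.2816)² × 4.1² / 1.1² = 292 per group, and 300 per group gives power 0.908. The stated sizing reproduces. The documents give no figure for the supply rule beyond 33.3%.

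**2. Cut-off with supply counted to delivery.** For unbroken supply from enrolment week E to delivery week D, the ratio is (D − E)/D. It is below 1/3 when D < 1.5 × E.

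| Enrolled (weeks) | Removed if delivered before (weeks) |
|---|---|
| 16 | 24 |
| 20 | 30 |
| 22 | 33 |
| 24 | 36 |

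Example, enrolled at 24 weeks: delivery at 35 gives 11/35 = 31.4%, removed; delivery at 37 gives 13/37 = 35.1%, kept. With enrolment no later than 24.0 weeks and continuous supply, no term birth, no birth at 36 to <37 weeks, and no woman enrolled by 16 weeks who delivers at 24 weeks or later is removed. If 24 weeks is read as up to 24 weeks 6 days, the cut-off reaches about 24.86 × 1.5 = 37.3 weeks.

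**3. Cut-off with all dispensed kits counted.** Kits are one month at 0, 1 and 2 months and 16 weeks at 3 months, using months of 4 weeks or of 30.4 days. Removal is then before 32.0–32.7 weeks (enrolled at 24) and before 30.0–30.7 (at 22). For enrolment at 20 it is before 28.0 with 4-week months; with calendar months it is before 24.3 and again from 26.1 to 28.7.

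**4. Partly supplied women.** With only the three monthly kits, 12/D < 1/3 when D > 36.0, or 13.03/D < 1/3 when D > 39.1. These women are removed for delivering late. Shipment limits how often this happens.

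**5. Illustrative size.** The documents give no enrolment-week or delivery-week distribution, so everything here is assumed: 5% of control births at 24–34 weeks; 8% at 34–37; losses before 24 weeks of 0 or 2.5%, equal in both arms; term births normal (39.2, SD 1.1) truncated to 37–42; flat or rising preterm tails; enrolment uniform over 8–24 weeks; continuous supply counted to delivery. Results are by exact integration over delivery week.

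The rule removes 1.2–2.8% of control women and 22–36% of births at 20 to <34 weeks.

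- **(a) 30% fewer births at 24 to <37 weeks.** The mean difference falls from 0.206–0.245 to 0.177–0.200 weeks (80–87% kept), and 90–94% of the absolute preterm difference is kept. Without losses, the same share of preterm births leaves each arm, so the odds ratio is (0.091/0.909)/(0.130/0.870) = 0.67 before and after; with losses, 0.70–0.71 becomes 0.69. The standard error of the log odds ratio rises 4–10%. The SD of gestational age also falls, so the test statistic for the mean is 0.92–1.11 of its unselected value.
- **(b) 30% of births at 36 to <37 weeks moved to term.** 101–103% of the mean difference is kept.
- **(c) Births at 24 to <32 weeks delayed by 4 weeks, all still preterm.** 40–52% of the mean difference is kept, and the odds ratio moves from 1.00 to 1.04–1.06, so a benefit can look like harm.

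Variations on (a), mean difference kept: dispensed kits counted, 86–93%; all enrolled at 16–24 weeks, 60–72% (dispensed 71–85%); all enrolled at 8–20 weeks, 93–98%.

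**6. Against the precision of the trial.** The interim table implies an SD of √(n × 0.953² / (2 × 2.80²)): 4.53 for n = 354 and 4.40 for n = 334. At 375 per arm the SE is 4.4 × √(2/375) = 0.32 weeks. The assumed distributions have SD 2.3–3.6, which gives SE 0.17–0.26. The loss in (a), 0.03–0.05 weeks, is small against any of these.

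**The case against.** The strongest reply concerns size. In the proportional-reduction scenario the shift is 0.03–0.05 weeks, the odds ratio hardly moves and power barely changes. In scenario (b) nothing is lost. Only the constructed scenario (c) shows a large distortion. The size also depends on late enrolment: Protocol 3 aims at the late first to mid second trimester, and with enrolment at 8–20 weeks almost all of the effect is kept. Birth outcomes are secondary, ITT analyses are planned, and a minimum-exposure rule is a recognisable aim for a per-protocol-type set. The interim definition served only sample-size re-estimation, so a different final definition is not in itself a contradiction.

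Most of this stands and limits the severity. The direction is also not universal: scenario (b) is not attenuated, and partly supplied women can be selected the other way, which was not modelled.

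It does not remove the defect. ITT is ranked second, so the headline birth estimate remains the selected one. Applying the same rule to both arms gives expected balance only if treatment does not affect timing of birth, which is the hypothesis under test. The rule is also a poor measure of exposure. A woman enrolled at 8 weeks and delivered at 36 with 12 weeks of product scores 12/36 = 33.3% and stays, despite 16 unsupplied weeks. A woman enrolled at 24 and delivered at 31, never without product, scores 7/31 and goes.

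**Conclusion.** The concern holds. As written, criterion 2(b) makes the primary set for the birth outcomes depend on gestational age at delivery. This follows from the wording and algebra alone, and under either reading of supply, late-enrolled women who deliver early are removed.

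The size in this trial is unknown. On the assumptions shown, a small share of women is lost, concentrated among the earliest births. Among continuously supplied women the mean difference and the absolute preterm difference are generally pulled toward zero, with the exceptions shown. The assumed control mean (38.1–38.6) is close to the interim 38.1, but the assumed SD is below the 4.4–4.5 implied there, so the true effect could be larger or smaller. Birth weight and time-to-event analyses were not computed. The primary Löe-Silness test has its own supply criterion and is untouched. This should be fixed, but it does not threaten the trial's primary conclusion.

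**What to change.** Before unblinding, which SAP 5.5 allows for, do one of the following:

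- **Drop 2(b) for birth outcomes.** This is the cleaner option.
- **Change the denominator** to the time from randomisation to delivery, count supply only up to delivery, and restate the threshold, for example the two thirds used at the interim. A continuously supplied woman then scores 100%. Even with nothing sent after the Month 3 kit she scores at least 28/34 = 82% (enrolled at 8 weeks, delivered at 42), so none is removed for delivering early.

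The second option is not fully clean. For partly supplied women, any rule that ends at delivery still depends on the outcome: at two thirds, a woman enrolled at 20 weeks with 12 weeks of product stays if she delivers by 38 weeks (12/18) and is removed if later.

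Under either option, report the planned ITT birth analyses with equal prominence. The cost is SAP wording and at most one derived variable, with no new data. The downside is that a few women with short exposure stay in the evaluable set.
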